#### *CP Women participants' and CP Facilitators' data collection.*

CP Women: At baseline and prior to the first (Maternal) of the two modules, participants will complete questionnaires, saliva sample collection, and a dental exam. These

activities will be scheduled for completion at the CP clinic site, outside of CP group scheduled time. A trained calibrated dental examiner will complete the dental exams in a private space, using portable dental equipment: chair, lamp, and stools. Study staff will administer the questionnaires and enter results directly into a tablet or laptop. The dental exam takes about 15-20 minutes and the questionnaires take about 15 minutes.

*The Maternal Intervention Module.* Intervention groups will receive the CPOP maternal intervention as part of their 3rd CP group session. Refer to Section 6.5 for details.

Approximately 10 weeks following the time of the maternal module and prior to the infant intervention module, participants complete the post-maternal module assessments consisting of a repeat dental exam and questionnaire completion. At this time, women also complete the pre-infant intervention module assessments. These consist of questionnaire assessment of infant OH knowledge and attitudes. Women receive their incentives within a week following completion of the assessments.

*The Infant Intervention Module.* The infant module is presented as part of the 7th or 8th CP session. Refer to Section 6.5 for details.

Approximately 2 weeks following the presentation of the Infant OH module, participants complete the post-infant OH module questionnaire assessment, repeating the earlier pre-module assessment. This may be done online with REDCap, email, or over the phone with an interview process. Women receive their incentives within a week following completion of the assessments. This is the final activity to occur during the prenatal period. Participants will receive a note from the study thanking them for their participation up to this point and reminding them that we will stay in touch with them about the study and will follow-up with them when their infants are about 10 months of age to schedule the 12-month postpartum visit.

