2. Gingival assessment: Gingival status will be assessed with full-mouth exams by measuring gingival recession and probing pocket depth to derive periodontal clinical attachment levels; and gingival bleeding on probing at baseline and post maternal module intervention. Changes in gingival status related to changes in oral hygiene (probing pocket depth and bleeding on probing) can be detected within the time frame we have designated for our pre-post dental examination. While attachment levels will be measured at baseline to characterize the sample, only probing pocket depth and bleeding on probing (not attachment levels) will be measured at mid-study post-maternal intervention.
3. Need for treatment and referrals for dental care: Though not a study outcome measure, as an obligation and service to the participants we will determine the need for treatment based on the protocol detailed in the Basic Screening Survey (BSS) developed by the Association of State and Territorial Dental Directors (ASTDD). For adults, the indicators include cavities, adults with one or more of their own teeth (as opposed to false teeth), and urgency of need for dental care.

Criteria for determining dental treatment need are the following:

Category	Recommendation for next dental visit	Criteria
Code 2: Urgent or emergency need for dental care	As soon as possible	Signs or symptoms that include pain, infection, swelling, or soft tissue ulceration of more than two weeks duration (determined by questioning)
Code 1: Early dental care is needed	Within several weeks	Caries without accompanying signs or symptoms, individuals with spontaneous bleeding of the gums, suspicious white or red soft tissue areas, or an ill-fitting denture are coded “1”
Code 0: No obvious problems	Routine dental care (next regular checkup)	Any patient without above problems

Oral health status information and recommendations for dental care will be provided to the participant along with a list of local dentists/dental clinics accepting Medicaid insurance and pregnant patients.

- Saliva collection: Saliva will be collected from the mother at baseline and both mother and baby at 12 months postpartum. It will be carried out by the CRA at a location and time convenient to the participant. The CRA will be trained in the following salivary collection techniques by Co-Investigator [name].

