### ***8.2.2    Special Assays or Procedures - Salivary bacterial analysis***

Microbiological assays: Salivary assays will be performed under the guidance of [name] in her laboratory at UCSF. Maternal and infant saliva will be assayed for *Mutans Streptococci* (MS), *Lactobacillus* (LB), and Total Viable Count (TVC).

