Primary Analyses will include intention-to-treat comparisons. The multilevel data structure will be accommodated by generalized linear mixed models (GLMMs) with random intercepts for CP centers, facilitators, groups, mothers/children, and repeated assessments (for maternal outcomes; PROC GLIMMIX). Main outcomes include binomial indicators of mothers' BOP (# sites bled/# sites probed) and PD4 (# sites with  $\geq 4$ mm pocket depth/# sites probed,) continuous indicator of maternal plaque levels, and a binary outcome of child oral MS colonization (multilevel logistic regression via Laplace estimation); and a count of child MS colonization (multilevel zero-inflated Poisson or a zero-inflated negative-binomial model, as appropriate, via Laplace). Each maternal outcome will be regressed onto indicators of experimental groups and assessment time, as well as the group-by-time interaction. Child MS outcomes at 12-months will be regressed onto the experimental group indicator. Significant intervention group main effects at follow-up and group-by-time interaction effects will be interpreted and described. If any key demographic or risk factors are imbalanced at baseline, we will include a quintile-stratified propensity adjustment, which can significantly reduce bias. Propensity scores will be estimated by regressing the intervention group indicator onto baseline characteristics of participants (averaged up to the unit of randomization); covariate balance across groups will be assessed. Next, propensity score quintiles will be formed. Regression models will initially include a quintile-by-groups-by-time interaction term to test whether the intervention effect is equivalent across quintiles. A significant interaction term would suggest quintile-specific treatment effects, which would then be estimated and reported. If the interaction term is non-significant, then it would be removed and the intervention effect estimated, conditional on the propensity-quintile main effect.

Secondary analyses will include multilevel linear models of secondary outcomes: OH knowledge, self-efficacy, importance, behavior scores; and multilevel binary and zero-inflated count outcome models of child LB and TVC levels. Additional multilevel models will explore whether any intervention effects are moderated by maternal race/ethnicity,

language, socioeconomic status, CP site, and baseline maternal OH knowledge and behaviors.

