### **16.2 Data Capture Methods**

**Questionnaires will be self-administered in English or Spanish directly into REDCap with either the text presentation or upon request administered to them through an interview process. Dental exam results will be directly entered into an Access database that will be saved in Excel spreadsheets and then uploaded into the REDCap system. Any system modifications or refinements will be validated. Later, lab results of salivary assays,**

**including levels of MS, LB, and TVC, will be recorded in Excel spreadsheets as CFU/ml along with sampling date, processing date, counting date, and then uploaded into REDCap.** **16.3 Types of Data**

Informed consent will be collected electronically except in the cases of no internet access when paper consents will be used and stored as the source document. Electronic case report forms will include dental examination data (periodontal measurements, plaque levels, caries prevalence), questionnaire responses, and salivary assay data as well as completion of intervention and assessment activities.

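### The infant MS model has arm as its only unconditional fixed effect; the mother's own baseline salivary MS, already collected and assayed, could be a prespecified covariate for a small gain

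*Combined protocol and SAP*

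**What the plan says.** Section 12.4 fits infant MS at 12 months with a multilevel logistic model that has random intercepts for centre, facilitator and group. Its fixed part is one sentence: "Child MS outcomes at 12-months will be regressed onto the experimental group indicator". The same sentence governs "a count of child MS colonization (multilevel zero-inflated Poisson or a zero-inflated negative-binomial model", which is not evaluated here.

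One further fixed effect is possible, but only on a condition: "If any key demographic or risk factors are imbalanced at baseline, we will include a quintile-stratified propensity adjustment". The propensity score behind it is built from "baseline characteristics of participants (averaged up to the unit of randomization", that is, from averages for 14 facilitators.

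The maternal measure exists. Section 4 places it ahead of any intervention: "At baseline and prior to the first (Maternal) of the two modules, participants will complete questionnaires, saliva sample collection, and a dental exam". Section 8.1 confirms the schedule: "Saliva will be collected from the mother at baseline and both mother and baby at 12 months postpartum". Section 8.2.2 adds "Maternal and infant saliva will be assayed for" MS, LB and total viable count, and section 16.2 has "levels of MS, LB, and TVC, will be recorded in Excel spreadsheets as CFU/ml". Table 1 (section 8.1) and Appendix A classify maternal bacteria as descriptive, and section 12.4 does not list them among the moderators.

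Section 2.1 gives the prognostic argument: infants get these bacteria chiefly from their mothers, and mothers above 10^5 CFU/ml are more likely to pass them on. It gives no odds ratio or correlation.

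**The concern.** The plan measures, before the first module, the factor that its own background section treats as the main source of the infant outcome, and then does not use it in the infant analysis. A prognostic baseline covariate normally sharpens the arm comparison in a randomised trial, and fixing it in advance removes a choice that would otherwise be made with data in hand.

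The propensity step does not fill the gap. Maternal MS could be taken as a risk factor under it, but section 12.4 does not define which factors are key or what counts as imbalanced, so the decision follows inspection of the data. Averaging to the facilitator also discards the mother-to-own-infant link, which is where the prognostic information lies. Nor does the restricted randomization in section 5.4.1 do this job: it used descriptive data on sites, facilitators and the populations they serve, before these women were enrolled.

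At stake are a little precision for Primary Aim 2 and a clear answer if the arms turn out to differ in maternal MS.

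**Working it through.** **Inputs from section 12.2.** 392 dyads, 75% retained, two-sided alpha 0.05, 49 groups of 8, facilitators split 8 and 6, group ICC 0.04, infant MS 24.9% v 10.9% (OR 2.71, power 0.80).

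**Inputs assumed, because the documents give none.** The share of mothers with high MS (40%, varied from 25% to 60%) and the maternal odds ratio for infant MS (1.5 to 6, equal in both arms).

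**Step 1: the plan's own figure.**
- Odds ratio: (0.249/0.751)/(0.109/0.891) = 2.71, as stated.
- Retained infants: 392 × 0.75 = 294, split 8:6 as 168 and 126, with 8 × 0.75 = 6 per group.
- Design effect: 1 + (6 − 1) × 0.04 = 1.20, so the effective numbers are 140 and 105.
- With 8 intervention facilitators the pooled rate is (105 × 0.249 + 140 × 0.109)/245 = 0.169. The null and alternative standard errors are 0.0484 and 0.0497.
- Power = Φ[(0.14 − 1.96 × 0.0484)/0.0497] = 0.818. With 6 intervention facilitators it is 0.805.

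This is within 2 points of the stated 0.80. The match depends on the design effect: 1.60, which adds all the ICCs, gives 0.702 and 0.680.

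**Step 2: the gain from adjustment.** Hold the marginal rates at 24.9% and 10.9%. Compute the expected information for the arm log odds ratio with and without a binary maternal term. Multiply the noncentrality for 0.80 power (2.80) by the ratio of the two z values: power = Φ(2.80 × ratio − 1.96).

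Example: odds ratio 4, 40% high, 168 intervention and 126 control.
- Infant risks for low and high mothers are 14.5% and 40.5% (control), and 5.5% and 19.0% (intervention). Check: 0.6 × 14.5 + 0.4 × 40.5 = 24.9.
- Arm only: log OR 0.997, SE 0.322, z 3.10.
- Adjusted: log OR 1.066, SE 0.334, z 3.19.
- The ratio is 1.031, so power = Φ(2.80 × 1.031 − 1.96) = 0.823.

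| Maternal OR | Conditional arm OR | Power (either arm larger) |
|---|---|---|
| 1.5 | 2.73 | 0.802 |
| 2 | 2.76 | 0.806–0.807 |
| 2.5 | 2.79 | 0.810–0.812 |
| 3 | 2.83 | 0.815–0.817 |
| 4 | 2.90 | 0.823–0.826 |
| 6 | 3.04 | 0.837–0.841 |

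With 25% or 60% high, power is 0.805–0.806 at odds ratio 2, 0.817–0.825 at 4 and 0.825–0.842 at 6.

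**Step 3: checks.**
- Unclustered simulation, 4,000 runs at 245 effective infants: +0.2 to +0.4 points at odds ratio 2, +0.8 to +1.2 at 3, +2.6 to +3.2 at 5. A useless covariate costs 0.4 points (0.826 to 0.822). Type I error is 0.050 adjusted and 0.051 unadjusted.
- Multilevel simulation with Laplace estimation (49 groups of 6, 600 to 700 runs): paired differences in power of −0.5 points (SE 0.8) at odds ratio 2, +2.1 (0.8) at 4 and +2.5 (1.2) at 6. At 2 the gain cannot be told from zero.
- Continuous covariate with odds ratio 1.25, 1.5 or 2 per SD: power goes from 0.818 to 0.821, 0.827 and 0.842, so +0.3, +0.9 and +2.4 points.
- Different strength by arm: odds ratio 4 in control and 1.5 in intervention gives 0.812–0.817, against 0.823–0.826 for a common 4.

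**The case against.** The best case against acting is that the gain may be close to nothing. The maternal sample is taken in pregnancy and the infant sample at Day 474 ± 90, and maternal levels can change in between. If 20% of high mothers are no longer high by then and equal numbers of low mothers become high, a true odds ratio of 4 looks like 2.5; if none become high, it looks like 3.2. The infant module also targets saliva sharing, so it may weaken the mother-infant link in the intervention arm. Both points stand, and they make the low end of the range credible.

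It can also be said that section 12.4 already permits adjustment for imbalanced risk factors. That is partial cover only, for the reasons given above.

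A reader might go further than the documents allow, in four ways:

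- **That the arm-only model is wrong.** Nothing shows this. Omitting a prognostic covariate from a randomised comparison is not an error, and section 12.2 reports simulations that support the modelling framework.
- **That the stated 0.80 is confirmed.** It is used here only as an anchor. With a t reference on 12 degrees of freedom, power at a design effect of 1.20 falls to about 0.74 or 0.70. The plan names no small-sample method, and this covariate would not address that.
- **That protection from chance imbalance is a separate benefit.** Such movement is already in the unadjusted standard error, so removing it is largely the same precision gain.
- **That the propensity quintiles would often contain a single arm by chance.** Counting random splits does not show this, because quintiles are ordered by predicted arm.

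**Conclusion.** The point holds as an optional refinement. Arm is the only unconditional fixed effect for infant MS. A pre-intervention measure of the protocol's own named source is collected and left as descriptive, and the conditional propensity step does not replace it.

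In power, the benefit is about 0 to 1 point for a maternal odds ratio up to 2.5, about 1.5 points at 3, and about 2 to 4 points at 4 to 6. These figures assume 40% of mothers high, one odds ratio in both arms, completers only, and arm-only power of 0.80. The strength of association is an assumption throughout. The firmer argument is prespecification: whether and how to adjust is settled before outcomes are seen.

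The covariate is measured after facilitators are randomised and, under section 5.4, after they know their arm. It is still taken before the module, from women who do not yet know their arm, and assayed masked (section 5.4.2).

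**What to change.** In section 12.4, prespecify the mother's own baseline salivary MS as a covariate in the infant MS binary model, whatever balance is observed.

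- **Form.** Fix it before outcomes are seen: either log10 CFU/ml with a stated rule for no-growth samples, or the 10^5 CFU/ml cut-off from section 2.1. The calculations used a single binary or normal covariate, so a form with an extra no-growth term has not been evaluated.
- **Missing values.** Include the covariate in the planned multiple imputation.
- **Reporting.** Give a marginal (standardised) risk difference and odds ratio beside the conditional odds ratio, so that the result can be compared with 24.9% v 10.9%.
- **Sensitivity.** Keep the arm-only model.
- **Exclusion.** Do not adjust for the 12-month maternal sample, which is taken after the intervention.

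No new data are needed. The cost is SAP wording, plus some work on imputation, standardisation and one sensitivity analysis. The arm odds ratio becomes conditional, about 2.75 to 3.1 for a marginal 2.71, and about 0.4 points of power are lost if maternal MS proves unrelated to infant MS.

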#### ***5.4.1 Randomization Procedures***

CP Facilitators will be randomly assigned to either Intervention or Control arm according to a matched, restricted randomization plan. Intervention facilitators will receive CPOP training after assignment. Our primary concern is strengthening the basis for causal inference by establishing equivalent experimental groups at baseline. Randomizing 5 sites is not optimal and randomizing CP participants is not possible because the intervention is delivered to CP groups. Therefore, we have chosen to randomize 14 CP facilitators, using "restricted randomization" to ensure an acceptable level of balance across experimental groups at baseline (e.g., create two sets of CP facilitators balanced on preexisting variables describing relevant characteristics of CP sites, facilitators, and their served populations; then, randomize one set of CP facilitators to deliver CPOP and

the other to deliver usual care). Prior to randomization we will identify facilitators from our five clinical sites who agree to accept assignment as an Intervention or a Control facilitator. Once identified, we will collect descriptive data characterizing each participating CP site and facilitator, as well as the populations they serve; these data will be included in the restricted randomization process. Intervention facilitators will receive CPOP training approximately 2 months before site initiation.

Originally, we planned to randomize CP facilitators into two sets of equal size (i.e., 7 CP facilitators assigned to each set). However, with summary data in hand, preliminary restricted randomization solutions with equal set size failed to establish reasonable cross-set balance on variable describing characteristics of CP sites, facilitators, and their served populations. Next, we allowed for set sizes of with 8 and 6 CP facilitators, respectively. Allowing for an '8/6' split resulted in several restricted randomization solutions that balanced CP site, facilitator, and patient population characteristics within close tolerances. Therefore, we opted to randomize CP facilitators into two groups with one group including 8 CP facilitators and the other including 6 CP facilitators. Once a final '8/6' split was chosen, the study statistician flipped a coin to assign the two sets to CPOP Intervention versus usual care control.

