## 12.2 Sample Size Considerations

**Sample size estimate and power analyses.** We assume 80% power; two-tailed  $\alpha=0.05$ ; 75% retention at 12 months; binary outcomes describing maternal gingival 1) pocket depth  $\geq 4$ mm (PD4) and 2) bleeding on probing (BOP) at each probed site (max=168; in pilot data  $\bar{x}=159$  sites per participant); 3) a continuously coded maternal plaque index score (PI: range 0-4); and 4) a child-level binary MS colonization indicator. The PD4 and BOP data for mothers will have a 5-level nested structure with a) 5 CP sites, b) 2-5 CP facilitators per CP site for a total of 14 CP facilitators participating in the study, c) 3-4 CP groups per facilitator for a total of 49 CP groups with participants enrolled in the study, and, on average, e) 8 study-enrolled mother-child dyads per CP group, and f) 159 gingival probe sites per mother; the maternal PI data and the child-level MS data will share the first four levels. The total sample size estimate is 392 mother-child dyads (49 CP groups  $\times$  8 mother-child dyads/CP group results in a total of 392 month-child dyads). Power analyses assumed two randomized groups including 8 and 6 CP facilitators, respectively. From our pilot data, we estimated intra-cluster correlations (ICC) for maternal PD4 equal to 0.001 for CP sites, facilitators, and groups, as well as 0.13 for CP women; ICCs for BOP equaled 0.04 for CP sites, facilitators, and groups, as well as 0.27 for CP women; ICCs for maternal PI equaled 0.13 for sites and 0.14 for facilitators and groups; ICCs for the child MS outcome equaled 0.01 for CP sites and CP facilitators as well as 0.04 for CP groups.

	observed effect in pilot	min. detectable effect
BOP: Ctrl v Intv (mothers)	16.7% v 10.7% OR=1.67, power>0.97	16.7% v 11.8% OR=1.50, power=0.80
PD $\geq 4$ mm: Ctrl v Intv (mothers)	20.4% v 17.0%* OR=1.25, power=0.80	20.4% v 17.0%* OR=1.25, power=0.80
PI (means) Ctrl v Intv (mothers)	0.95 v 0.76 d=0.41, power=0.89	0.95 vs 0.78 d=0.37, power=0.80
MS: Ctrl v Intv (children)	24.9% v 6.5% OR=4.77, power=0.97	24.9% v 10.9% OR=2.71, power=0.80

\* observed and minimum detectable effects equivalent w/in rounding;  
d represents a group difference of standardized means

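### If propensity quintiles are used, an interaction pre-test decides whether a maternal primary outcome is reported as one overall effect or five quintile effects; the overall effect should be primary either way

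*Combined protocol and SAP*

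**What the plan says.** Section 12.4 (Final Analysis Plan) fits each maternal outcome on arm, time and arm-by-time, and child MS at 12 months on arm. If key demographic or risk factors turn out imbalanced at baseline, a propensity adjustment in quintiles is added. The score is built from participant characteristics averaged to the randomized unit, the facilitator.

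Three consecutive sentences then set the rule:
- The test: "Regression models will initially include a quintile-by-groups-by-time interaction term to test whether the intervention effect is equivalent across quintiles".
- If significant: "A significant interaction term would suggest quintile-specific treatment effects, which would then be estimated and reported".
- If not: "If the interaction term is non-significant, then it would be removed and the intervention effect estimated, conditional on the propensity-quintile main effect".

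Section 5.4.1 gives the number of units: "Therefore, we opted to randomize CP facilitators into two groups with one group including 8 CP facilitators and the other including 6 CP facilitators". Section 12.2 sizes the trial for the arm comparison: "The total sample size estimate is 392 mother-child dyads", and "Power analyses assumed two randomized groups including 8 and 6 CP facilitators, respectively". Section 12.1 states Primary Hypothesis 1 as a comparison of CPOP with usual care on each of three maternal outcomes. It says nothing about propensity strata.

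The plan gives no power for the interaction test, no margin for calling effects equivalent, no multiplicity rule for five quintile effects, and no statement of which result is primary when the test is significant.

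**The concern.** Once the propensity step is entered, the form of the primary result depends on the data through a test the trial was not sized for. There are two consequences.

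First, the test is said to examine whether effects are equivalent. A non-significant interaction test supports that only if it would probably have detected differences that matter. With two or three facilitators per quintile, and one or two per quintile-by-arm cell, that is doubtful.

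Second, when the test is significant, including by chance, the plan commits to five unadjusted contrasts and is silent on the one comparison that Primary Hypothesis 1 asks for. Five contrasts selected because they differ will nearly always include one that looks significant. The chance of a false claim then exceeds 5%, and the primary question may be left without a stated answer.

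This does not depend on quintiles that are empty or hold one arm only. That is a separate difficulty, and every calculation here assumes both arms are present in every quintile.

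**Working it through.** **Inputs.** Section 12.2: 80% power, two-tailed 0.05, 49 groups of 8, 75% retention at 12 months, 8 and 6 facilitators, minimum detectable effect (MDE) per outcome. Section 12.4: five quintiles, and two time points for maternal outcomes. Assumed: the spread of effects across quintiles, and any clustering of change. The documents give neither.

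**1. The plan's own figures.** 49 × 8 = 392 dyads, as stated. For child MS, 0.75 × 392 = 294 children, split 168 and 126. With 6 per group and a group ICC of 0.04, the design effect is 1 + 5 × 0.04 = 1.20. A two-proportion calculation for 24.9% v 10.9% gives power 0.805 (stated 0.80), and for 24.9% v 6.5% gives 0.979 (stated 0.97). Adding the facilitator ICC of 0.01 lowers the first to 0.756–0.773. The maternal powers came from multilevel simulation and cannot be recovered by a simple formula. The next steps therefore take the stated 80% at the MDE as given.

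**2. Power of the interaction test.** Degrees of freedom: (5 − 1) × (2 − 1) × (2 − 1) = 4. At the MDE the overall effect has noncentrality (1.960 + 0.842)² = 7.85. With five equal quintiles, each quintile effect has five times the variance of the overall effect, so the interaction noncentrality is 7.85 × (SD of quintile effects ÷ MDE)². The mean effect is held at the MDE. The F(4,4) column is a facilitator-level bound, with 14 facilitators − 10 cells = 4 residual df.

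| Quintile effects (× MDE) | SD ÷ MDE | Noncentrality | Power, chi-square(4) | Power, F(4,4) |
|---|---|---|---|---|
| 0.5, 0.75, 1, 1.25, 1.5 | 0.354 | 0.98 | 10% | 7% |
| 0 in one, 1.25 in four | 0.500 | 1.96 | 17% | 9% |
| 0, 0.5, 1, 1.5, 2 | 0.707 | 3.92 | 31% | 14% |
| 0, 0, 1, 2, 2 | 0.894 | 6.28 | 49% | 20% |
| −1, 0, 1, 2, 3 | 1.414 | 15.70 | 91% | 43% |

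By chi-square, power passes 50% only when the SD exceeds 0.90 × MDE, and reaches 80% at 1.23 × MDE. A simulation at the level of the women (392 women, 8/6 facilitators, no clustering of change) misses differences spanning 0.5 SD in 76% to 78% of trials.

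**3. False positives under the rule, with no effect in any quintile and no clustering of change.** The overall estimate and the interaction statistic are independent, so:
- test not significant, overall effect significant: 0.95 × 0.05 = 0.0475;
- test significant, at least one quintile effect at |z| > 1.96: 0.05 × 0.955 = 0.0478, where 0.955 is simulated;
- total: 0.0475 + 0.0478 = 0.095 per outcome.

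Direct simulation gives 0.095, and simulation at the level of the women gives 9.5% to 10%. Always using the overall effect gives 0.050.

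**4. Cost when there is one common effect at the MDE.** The chance that the overall effect is both reported under the rule and significant is 0.95 × 0.80 = 0.76, against 0.80. In the significant branch, each quintile has only 24% power at the MDE.

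**5. If change clusters by facilitator and the model ignores it.** At an assumed facilitator ICC of change of 0.01, the rule gives about 18% and the overall effect alone about 8%. Both exceed 5%; only the gap between them is due to the rule.

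**The case against.** Several points on the other side are sound.

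- **The step is conditional.** It applies only if baseline imbalance is found, and section 5.4.1 describes a restricted randomization chosen for close balance. The step may never be reached. But no threshold for imbalance is given, so entry is itself a judgement made on the data.
- **A reader might infer that the overall effect is withdrawn when the test is significant.** The text does not say that. Section 12.4 first describes the arm and arm-by-time effects without condition, and nothing forbids reporting them as well. What stands is that, within the adjusted analysis, the plan commits to an overall effect in one branch only and does not say which result is primary in the other.
- **A reader might infer that the plan declares effects equivalent after a non-significant test.** It does not. The word describes what the test is for; the non-significant branch only drops the term. The point is that the test cannot serve that stated purpose.
- **A reader might attribute error rates near 20% or higher to the pre-test.** Such rates appear only with assumed clustering of change that the model ignores, and the overall test is then also above 5%. That is a separate question of model specification, which the fix below does not cure.
- **A reader might extend the figures to child MS.** The term contains time and the child model has none, so the documents do not say what would be tested there. No error rate for child MS is claimed.
- **Low power depends on the assumed spread.** Very large or sign-changing differences would often be found by the chi-square test.

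**Conclusion.** The concern holds, within the limits above, and should be corrected. If the propensity adjustment is used, an interaction test on 4 df chooses between one overall effect and five quintile effects for each maternal primary outcome, although the hypothesis and the sample size concern only the overall effect.

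Per outcome, with no effect and no clustering of change, the rule about doubles the chance of a nominally significant claim, from 5% to about 9.5%–10%. With a common effect at the MDE, it lowers the chance of a reported and significant overall effect from 80% to 76%. Power to detect differences between quintiles is about 10% to 31% for spreads up to 0 to 2 × MDE, and 7% to 14% on the facilitator-level bound.

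These figures assume equal quintiles that each contain both arms, the stated 80% power at the MDE, and no multiplicity adjustment across quintiles, as none is stated.

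**What to change.** In section 12.4, replace the two-branch rule with three statements:

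1. When the propensity adjustment is used, the primary result for each outcome is always the single overall arm effect (arm-by-time for maternal outcomes, arm for child MS), conditional on the propensity-quintile main effect, whatever the interaction test shows.
2. The quintile interaction is exploratory. It is reported as estimates with confidence intervals that reflect variation between facilitators, and is described as exploring heterogeneity, not as testing whether effects are equivalent.
3. The same rule applies to child MS, where the exploratory term is quintile-by-arm because the model has no time term.

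The cost is a few sentences of plan text, with no extra data, visits or participants. The small downside is that real differences by propensity quintile would be reported as exploratory, not primary.
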